1 CUHK Achilles Tendon Disorder Registry

2 **Research Project Statement**

3 The Achilles tendon is one of our body's most important structures, and the 'Achilles heel' is
4 a real clinical problem. The management of its pathologies—spanning acute ruptures to
5 chronic tendinopathies—remains heterogeneous, with a critical absence of high-quality
6 longitudinal data to compare treatments and guide personalized rehabilitation strategies. To
7 address this evidence gap, we will establish a comprehensive prospective Achilles Tendon
8 Disorder Registry.

9 The registry will integrate our team's expertise in Achilles tendon research, which
10 encompasses standardized assessment tools, biomechanical studies, and treatment evaluation.
11 By systematically collecting outcome data, it will enable us to: determine the effectiveness of
12 different treatment methods, advance evidence-based knowledge, improve the quality of care,
13 enhance patient safety, achieve better patient outcomes, and reduce healthcare costs. This
14 longitudinal registry will monitor long term outcome of Achilles tendon problem, and track
15 Achilles tendon treatment outcomes, thereby helping to inform precision rehabilitation
16 strategies and reduce long-term disability in the future.

17 **Research Questions**

- 19 1. Does the baseline status (e.g., vascularity and elastography metrics) influence the
20 prognosis?
- 21 2. Does pre-existing Achilles tendinopathy increase the risk of acute Achilles tendon rupture?
- 22 3. Which group of patients is more responsive to which treatment?

23 **Hypothesis**

- 25 1. Baseline status (e.g., vascularity and elastography metrics) significantly influences
26 prognosis.
- 27 2. Pre-existing Achilles tendinopathy significantly increases the risk of acute Achilles tendon
28 rupture.
- 29 3. Different patient groups respond differently to various treatment methods.

31 **Research Methodology**

32 **Study setting**

33 This prospective cohort study will be conducted at the Prince of Wales Hospital in Hong
34 Kong. All self-reported, functional, and ultrasonographic outcomes will be assessed at
35 baseline, 6 weeks, 3 months, 6 months, and 1 year. Following the initial 1-year follow-up, all
36 self-reported outcomes will be assessed annually through online questionnaires at 2, 3, 4, and
37 5 years. All participants must provide written informed consent prior to enrolment. The

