38 investigator will obtain and document consent before any study procedures are performed.
39 All eligible participants will be fully informed about the study and given ample time to
40 consider participation; the research team will answer all participant questions. The trial will
41 be conducted in accordance with the Declaration of Helsinki.

42 **Eligibility**

43 Inclusion:

- 45 • Adults (>18 years of age)

47

48 Exclusion:

49

50

51

52

53

54

- 55 Any physical or psychological comorbidity that would impair the ability to complete study assessments (e.g., significant neurological deficits) or preclude the provision of informed consent.
- Concomitant diseases that severely affect lower limb function or assessment (e.g., severe osteoarthritis of the knee or hip, prior lower limb amputation, peripheral vascular disease, active rheumatoid arthritis, lower limb paralysis, etc.)

56 **Outcome measures**

57 Baseline demographic data will be collected, including age (date of birth), gender (biological sex), occupation, recreational activity (Pre-injury and current activity levels -Tegner score), diagnosis (types of Achilles tendon problem) , treatment modalities already tried.

60 Time frames for collection include 0 weeks (baseline), 6 weeks, 3 months, 6 months, 1 year. Following the initial 1-year follow-up, all self-reported outcomes will be assessed annually through online questionnaires at 2, 3, 4, and 5 years.

64 **Primary Outcome: Victorian Institute of Sports Assessment (VISA-A) Questionnaire**

65 The primary outcome measure will be the Victorian Institute of Sport Assessment (VISA-A) questionnaire, available in either the original English or validated Chinese version, depending on the participant's native language. This specific scoring system developed for the Achilles tendon is the most widely used score for clinical Achilles research. The VISA-A is scored on a scale of 0 to 100; lower scores indicate more severity of symptoms, while a score of 100 indicates a healthy and pain-free Achilles tendon.

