72 **Secondary Outcomes: Numeric Pain Rating Scale (NPRS); Foot and Ankle Outcome Scores (FAOS); Achilles tendon resting angle (ATRA); Royal London hospital test; Calf Muscle Strength; Heel raise test; Jump test; Foot pressure distribution; Ultrasonographic tendon thickness; Ultrasonographic tendon cross-sectional area; Ultrasonographic neovascularity; Ultrasonographic tendon elasticity; Ultrasonographic calf muscle quality; Photoacoustic imaging-derived tendon oxygenation and vascularity; Thermographic tendon temperature.**

80 **Numeric Pain Rating Scale (NPRS):** The Numeric Pain Rating Scale (NPRS; 0–10, where 10 represents maximum pain) will be used to assess pain levels, as pain is the primary symptom of midportion Achilles tendinopathy. Participants will report their “Worst pain during sports in the past two weeks,” “Worst pain during daily activities in the past two weeks.”

86 **Foot and Ankle Outcome Scores (FAOS):** The FAOS is a validated patient-reported scoring system used for general foot and ankle problems. It is split into five categories: symptoms, pain, daily activities, sporting function, and quality of life. Scores range from 0 to 100, with 0 being the lowest and 100 being the highest.

90 **Achilles tendon resting angle (ATRA):** The ATRA will measure participants' tendon length/tension. Participants should be positioned in a prone position with the knee flexed to 90 degrees. The assessor will use a dynamic joint goniometer to measure the angle at which the foot passively falls.

94 **Royal London hospital test:** The Royal London Hospital Test is used to help diagnose mid-portion Achilles tendinopathy. The patient lies prone with the foot relaxed, and the examiner

96 palpates the most tender spot on the Achilles tendon. The patient then moves the ankle
97 through dorsiflexion and plantarflexion. A positive test occurs if tenderness decreases during
98 dorsiflexion.

99 **Calf Muscle Strength:** The hand-held dynamometer will be used to quantify isometric
100 muscle strength during ankle dorsiflexion and plantarflexion. Participants will maintain
101 maximal isometric contraction for 3 seconds. Three trials will be recorded for each movement,
102 with 30-second rest intervals between trials to prevent fatigue.

103 **Heel raise test:** Participants will be instructed to keep the knee straight and rise as high as
104 possible on the toes each time until fatigue. Participants can place two fingertips per hand on

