105 the wall to maintain balance. The rhythm will be set at a frequency of 30 heel rises per
106 minute by following a metronome. Total test duration (in seconds) will be recorded.

107 **Jump test:** Participants will perform three one-legged counter-movement jumps on a
108 pressure mat (Tekscan, USA) with jump height (cm) calculated from flight time. After
109 demonstration and submaximal practice jumps, the patient executed maximal jumps from a
110 standing position by rapidly squatting (flexing knee/hip/ankle) before exploding upward. The
111 highest jump was recorded, with NPRS-reported Achilles tendon pain immediately post-test.

112 **Foot pressure distribution:**

113 In foot pressure distribution examination, the scan (Tekscan, USA) will be masked and
114 divided the foot into eight regions including both forefoot, midfoot and hindfoot: hallux,
115 lesser toes, lateral and medial forefoot, lateral and medial midfoot, lateral and medial
116 hindfoot. Peak pressure and impulse in each region will be calculated to see the before-and-
117 after change. Additionally, the centre of pressure excursion index (CPEI) will also be
118 calculated to which reflects the excursion of the centre of pressure. The first and last points of
119 a centre of pressure curve will be connected to construct a line measured in the distal tertile
120 of the foot and normalized by the foot's width.

121 **Zebris Treadmill Gait and Stance Analysis:** The Zebris is a treadmill equipped with
122 advanced pressure sensors designed to analyze gait and stance. Subjects were instructed to
123 walk barefoot on the treadmill at their comfortable pace while maintaining a natural walking
124 pattern. During the test, the pressure distribution across the plantar surface of the feet was
125 recorded, capturing dynamic data such as force, timing, and spatial parameters of each step,
126 which ensures precise measurement of walking and stance characteristics, providing valuable
127 insights into balance, weight distribution, and movement symmetry for clinical or research
128 purposes.

129 **Achilles Ultrasonography:**

130 To ensure reproducibility, a standardised Achilles tendon ultrasound imaging protocol will be
131 used to perform the assessment at all time points in the trials. Subjects will lie prone on the
132 examination table with knees straight and ankles hanging in a relaxed position. The Achilles

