221 variables will be presented as frequencies and percentages.222 To address Q1 (prognostic influence of baseline status), multivariable linear or logistic
223 regression models will be constructed to evaluate the association between baseline metrics
224 (e.g., vascularity, elastography) and functional outcomes (e.g., VISA-A, heel raise capacity),
225 adjusting for covariates such as age, sex, and symptom duration.226 For Q2 (risk assessment), a Cox proportional hazards model or logistic regression will be
227 used to examine whether pre-existing tendinopathy (dichotomized: yes/no) predicts
228 subsequent acute rupture, with results reported as hazard ratios or odds ratios and 95%
229 confidence intervals.230 For Q3 (treatment responsiveness), interaction terms between patient subgroups (e.g., defined
231 by baseline severity, structural metrics) and treatment types will be incorporated into
232 regression models to identify effect modifiers. Should significant interactions be detected,
233 stratified analyses will be performed.234 **Interim analyses:** An interim analysis will be performed on the primary endpoint when 20%
235 of participants completed the 1-year follow-up. The interim analysis ensures that no serious
236 adverse event happened during the study period.237 **Methods in analysis to handle protocol non-adherence and any statistical methods to
238 handle missing data:** Missing data will be handled using multiple imputation under the
239 missing-at-random assumption. Sensitivity analyses will include complete-case assessments.
240 Model assumptions (e.g., linearity, proportionality) will be verified graphically and
241 analytically.242 **Plans to give access to the full protocol, participant-level data, and statistical code:** The
243 protocol will be registered on clinicaltrials.gov. The participant-level data and statistical code
244 can be provided upon request.

245 **Oversight and monitoring:** The principal investigator will monitor the progress of the study.
246 The trial steering committee consists of research team members who will participate in
247 participant recruitment, data collection, and management. The trial steering committee
248 consists of orthopaedic surgeons and researchers (research assistants and biostatisticians).
249 The orthopaedic surgeons and research assistants will participate in data collection and
250 analysis. The biostatistician will monitor data collection and perform interim analysis. There

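### Heel-raise and jump tests have no score for a participant who cannot do them because of the tendon, while one missing-at-random rule covers every missing value

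*Protocol*

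**What the plan says.** - **Scope.** The Research Project Statement describes the field that the registry is set up to cover: "The management of its pathologies—spanning acute ruptures to" chronic tendinopathies.
- **Schedule.** Study setting: "All self-reported, functional, and ultrasonographic outcomes will be assessed at" baseline and four later visits. Outcome measures repeats the times: "Time frames for collection include 0 weeks (baseline), 6 weeks, 3 months, 6 months, 1 year". Neither place varies the schedule by diagnosis.
- **Tests.** In the heel raise test the participant rises as high as "possible on the toes each time until fatigue", and the result is a time: "Total test duration (in seconds) will be recorded". For the jump test, "Participants will perform three one-legged counter-movement jumps on a" pressure mat, and the best height in cm is kept. Neither description says what to enter for a person who cannot do the test.
- **Use in the analysis.** The Q1 paragraph of the statistical methods relates baseline metrics to function ("e.g., vascularity, elastography) and functional outcomes (e.g., VISA-A, heel raise capacity"). Q3 adds interactions between treatment and subgroup to regression models, without naming the outcomes.
- **Missing data.** "Missing data will be handled using multiple imputation under the" missing-at-random assumption. No distinction is made by reason, and complete-case analysis is the only sensitivity analysis named.

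**The concern.** A heel-raise time or jump height can be absent because of the very thing it measures: the tendon is too impaired for the test. Such a blank carries information, and it differs from a missed appointment. Missing-at-random imputation fills it from the relation seen among people who completed the test. Complete-case analysis drops the person. Both therefore describe function as if inability did not occur, and because they err in the same direction, their agreement would be read as reassurance.

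At stake are the level of performance reported for the cohort, the Q1 association between baseline status and heel-raise capacity, and any Q3 comparison of function between treatments. If worse baseline status makes inability more likely, which is the direction Hypothesis 1 suggests, the part of the association that runs through inability is lost.

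This is also a data-collection matter. If the assessment form does not record why a test is absent, a later analysis plan cannot reliably recover the reason.

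**Working it through.** The protocol gives no figure to reproduce: no share unable, no heel-raise mean or SD, no imputation model. Every input below except n = 500 (the minimum recruitment in Sample size) is an assumption, and inability is scored 0 s for illustration.

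**1. Simple bound on the mean.** Let a share u be unable (value 0) and let the others average m. The cohort mean is (1 - u)m. Complete-case analysis, or imputation with no useful predictor, reports about m. The overstatement is 1/(1 - u) - 1:
- u = 10%: 1/0.9 - 1 = 11%
- u = 30%: 1/0.7 - 1 = 43%
- u = 50%: 1/0.5 - 1 = 100%

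**2. Effect on a Q1 slope.** Simulation with n = 500. Baseline metric x is standard normal, with higher values worse. If able, y = 45 - 4x + N(0, 15²) seconds; if unable, y = 0; logit P(able) = c - 0.8x, with c set to give the share unable. Blanks are imputed from the able, given x.

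| Share unable | Slope, inability = 0 (s per SD) | Slope after imputation | Share of slope lost |
|---|---|---|---|
| 10% | -6.55 | -4.00 | 1 - 4.00/6.55 = 39% |
| 21% | -8.34 | -3.97 | 1 - 3.97/8.34 = 52% |
| 29% | -9.32 | -4.01 | 1 - 4.01/9.32 = 57% |
| 39% | -9.86 | -4.00 | 1 - 4.00/9.86 = 59% |

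Numerical integration of the same model gives -6.49, -8.38, -9.28 and -9.88 for the second column, in agreement. A separate run of the 10%, 29% and 39% cases gave a complete-case slope of -4.0 each time. Imputation and complete-case analysis agree with each other and both miss the target.

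**3. Does a richer imputation model repair it?** A second simulation with n = 500 assumed that ruptures are 10%, 25% or 40% of the cohort, that 70%, 90% or 100% of them are unable, and that the worst 5% of the others are unable. Able non-rupture participants average about 40 s with SD 15. Mean heel-raise time in seconds:

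| Ruptures; unable among them | Inability = 0 | Imputed: age | Imputed: age + VISA-A | Imputed: age + VISA-A + diagnosis | Complete case |
|---|---|---|---|---|---|
| 10%; 70% | 36.0 | 40.7 | 39.3 | 39.5 | 40.7 |
| 25%; 90% | 30.0 | 40.8 | 37.6 | 38.2 | 40.7 |
| 40%; 100% | 23.5 | 41.1 | 35.8 | 35.7 | 41.1 |

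In the middle row the overstatement runs from (37.6 - 30.0)/30.0 = 25% to (40.8 - 30.0)/30.0 = 36%. Over all nine combinations, the unable were imputed on average at 39.6 to 41.1 s with age alone, 28.4 to 30.1 s with VISA-A added, and 28.4 to 31.9 s with VISA-A and diagnosis. Better predictors reduce the error but do not remove it. When every rupture participant is unable at a visit, no rupture result exists and the imputation rests wholly on people without a rupture.

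**The case against.** **Inability may never be recorded as missing.** A duration or a jump height can be entered as 0, and the protocol does not say otherwise. This stands. A reader might infer that the plan imputes disabled patients as if they were able; the text does not say so. What it shows is an undefined score beside a general missing-at-random rule, so two assessors could enter 0 and a blank for the same result.

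**Much of this belongs in an analysis plan.** The content of the imputation model and further sensitivity analyses are commonly left there, complete-case analysis is not presented as the only one possible, and Q1 allows logistic models, so an able/unable analysis is compatible with the text. That is fair for the modelling detail. It does not cover the reason for absence, which must be captured at the visit, nor the protocol's own choice of one mechanism for all missing data.

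**The bias is partial, and its size is assumed.** This stands. Imputed values fall well below the able average once severity enters the model. The Q1 slope is attenuated, not abolished: it stays near -4.0. A treatment gap can be made to vanish (40% against 10% unable with equal means m among the able: 0.9m - 0.6m = 0.3m, reported as about 0), but only because equal means were assumed. The protocol fixes no visit for Q1, so bias at a given later visit is not demonstrated. For someone not tested on clinical grounds, 0 is a scoring convention and not an observation.

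**Safety.** A reader might infer that scheduling jumps for participants with acute rupture contradicts the document's own safety provisions. No section says that these tests are unsuitable after rupture, so there is no contradiction in the text. The schedule simply does not say whether it varies by diagnosis.

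**Eligibility.** The inclusion list breaks off after age in the available text. The scope therefore rests on the Research Project Statement, and nothing is concluded here from gaps in the criteria.

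**Conclusion.** The point holds as a conditional one and should be addressed. The protocol leaves inability because of the tendon unscored and applies a single missing-at-random rule to all missing data. If inability is left blank, that rule and the named sensitivity analysis both rest on people who could do the test. Heel-raise performance is then overstated and its association with baseline status is attenuated, by 39% to 59% in the illustration for 10% to 39% unable with a single-predictor imputation model. These percentages depend on the assumed shares, means and model, and on scoring inability as 0 s; a richer imputation model lowers the overstated mean without curing it.

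The reach is limited to secondary performance outcomes. Heel raise is an example outcome for Q1, the jump test is named in no analysis, and Q3 is affected only where function is modelled. A reader might infer that the primary result is compromised. The documents do not support that: VISA-A is a questionnaire and does not require the participant to perform these tests.

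**What to change.** 1. Add a reason code to each functional test at each visit: done; unable because of the tendon; not attempted on clinical grounds; missed visit or technical failure.
2. Define before analysis that inability because of the tendon is an outcome and is not imputed. Options are a two-part model (able or not, then performance among the able) or a worst-rank analysis.
3. Restrict missing-at-random imputation to missed visits and technical failures. State separately how tests not attempted on clinical grounds are handled, since they fit neither group.
4. Add a not-at-random (delta-adjusted) sensitivity analysis beside the complete-case one.
5. State how the all-visits schedule of functional tests applies to participants with acute rupture. Which test applies at which visit is for the investigators to decide.

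The cost is one form field per test and a few sentences in the missing-data section. The small downside is that a two-part or rank-based model is less simple to report than a mean difference in seconds. The field should be added early in the 2025 to 2028 enrolment, because reasons not recorded at the visit cannot be reliably reconstructed.

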191 includes school sports teams, professional organizations (e.g., Kitchee Football Club), and an
192 extensive alumni network of doctors and sports medicine professionals from our MSc
193 program. Simultaneously, study advertisements will be distributed to all staff and students of
194 The Chinese University of Hong Kong through the CUHK Mass Mail System to ensure
195 comprehensive outreach.

196

197 **Data collection and management**198 **Plans to promote participant retention and complete follow-up:** The schedule for all the
199 outcome measure appointments will be provided from the beginning. For patients who have
200 missed their scheduled appointments for follow-up assessments, additional hours will be
201 extended to the evenings at the Sports Performance and Biomechanics laboratory at CUHK
202 so that participants may come for assessment (e.g., after work, rescheduled due to illness,
203 etc.).204 **Data management:** Data collected will be securely stored in password-protected computers
205 and archived for five years after publication. The Principal Investigator (PI) and research
206 assistants will oversee data collection, entry, and analysis. To ensure accuracy, a double data
207 entry method and range checks will be implemented. Data will be restored into an Excel files
208 and then transferred to SPSS software for analysis.209 **Confidentiality:** To ensure the highest level of privacy and security, the Sports Performance
210 and Biomechanics Laboratory stores all personal information and consent forms in securely
211 locked cabinets. Our online electronic database is protected by password-protected computers,
212 ensuring the utmost confidentiality. Access to the collected data is strictly limited to trusted
213 trial team members, with no access granted to participants. De-identified participant data may
214 be shared with other researchers upon reasonable request and after execution of appropriate
215 data sharing agreements, subject to approval by the ethics committee.

216 There is no plan for using biological specimens outside of this study plan.

217 **Statistical methods for primary and secondary outcomes:** Statistical analyses will be
218 performed using SPSS (version 28.0), with a two-sided significance level of $\alpha = 0.05$.
219 Continuous outcomes (e.g., VISA-A, NPRS, tendon thickness, dynamometry) will be
220 summarized as mean \pm standard deviation, assessed by Shapiro–Wilk test. Categorical

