251 is no independent data monitoring committee, as the ethics committee does not require this.

252 **Adverse events reporting and harms:** The procedure will be supervised by orthopaedic
253 surgeons licensed under the Medical Council of Hong Kong. If a participant experiences a
254 severe adverse reaction to the intervention, it will be reported to the trial steering committee
255 immediately, and the participant will be removed from the trial.

256 **Frequency and plans for auditing trial conduct:** An independent auditor from the ethics
257 committee will conduct the trial conduct annually. The principal investigator will complete a
258 progress report form for the ethics committee to review conduct annually during the trial
259 period.

260 **Plans for communicating necessary protocol amendments to relevant parties:** The
261 investigators will seek protocol amendments from the ethics committee, which must approve
262 them before implementation. Trial participants will be notified of any changes to the protocol.
263 Furthermore, the protocol modifications will be publicly available in the Trial Register.

264
265 **Funding and Sponsors:**

266 There are no declared funding sources or sponsors at this stage.

267 **Institutional Affiliations:**

268 The study is conducted by the Department of Orthopaedics and Traumatology, Faculty of
269 Medicine, The Chinese University of Hong Kong (CUHK).

270 **Potential Conflicts of Interest:**

271 All investigators involved in this study have declared no competing interests.

272 **Incentives for Subjects:**

273 No financial or material incentives are provided for participation.

274 **Provisions for Harm:**

275 Participants who experience adverse effects directly attributable to the study will receive
276 appropriate medical care at the Prince of Wales Hospital, CUHK, at no additional cost.
277 Compensation for research-related harm will follow institutional and ethical guidelines.

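### A severe reaction to an undefined intervention removes the participant, and the protocol does not say that the planned 5-year questionnaires continue

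*Protocol*

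**What the plan says.** The rule stands in the Protocol under *Adverse events reporting and harms*. The trigger is described as a "severe adverse reaction to the intervention, it will be reported to the trial steering committee", and the sentence goes on: "immediately, and the participant will be removed from the trial". It carries no qualifier. The same paragraph opens with "The procedure will be supervised by orthopaedic" surgeons, without saying which procedure is meant. *Provisions for Harm* uses a third term: "Participants who experience adverse effects directly attributable to the study will receive" medical care.

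The rest of the protocol describes an observational study. *Study setting* calls it a prospective cohort. The *Research Project Statement* says that the "longitudinal registry will monitor long term outcome of Achilles tendon problem, and track" treatment outcomes, and it lists patient safety among the aims. All outcomes are measured at baseline, 6 weeks, 3 months, 6 months and 1 year. After that, all "self-reported outcomes will be assessed annually through online questionnaires at 2, 3, 4, and" 5 years.

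The retention plan, under *Data collection and management*, deals with participants who have "missed their scheduled appointments for follow-up assessments, additional hours will be" extended into the evening. The paragraph on non-adherence and missing data specifies multiple imputation under missing at random, with complete-case analysis as the named sensitivity analysis.

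**The concern.** In a trial of an assigned treatment, removal after a reaction might be understood as stopping that treatment while follow-up goes on. Here no treatment is assigned, so being in the study means being assessed. Removal then most naturally means that assessment ends.

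The participants concerned are selected by a severe reaction. They are among the most informative for a registry that sets out to follow long-term outcome and improve safety. Scores that are never collected cannot be recovered by any later analysis plan, so this is a matter of study conduct rather than of analysis detail. Because the trigger is undefined, site staff would also have to decide case by case when the rule applies.

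**Working it through.** **1. What the trigger could mean.** The protocol has no study intervention, and the word appears only in the removal sentence. Two readings are open.

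- *Treatment received.* Treatment types enter the analysis of the third research question, so a reaction to treatment is a natural meaning.
- *Study assessments.* *Procedure* is used elsewhere for study procedures (the consent paragraph, the thermography description), and *Provisions for Harm* speaks of effects attributable to the study.

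The text does not settle which is meant, or whether both are.

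**2. Whether any section keeps follow-up going after removal.**

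- Retention plan: missed appointments only.
- Non-adherence and missing data: imputation of what is missing, with nothing on continued collection.
- *Provisions for Harm*: medical care and compensation only.

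None of them separates removal from the end of data collection.

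**3. What one removed participant loses.** Inputs are the visit times in *Study setting* and *Outcome measures*. VISA-A is self-reported, so it is due at 0, 6 weeks, 3 months, 6 months, and 1, 2, 3, 4 and 5 years: 5 + 4 = 9 assessments. Scores lost = 9 − scores obtained.

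| Last visit before removal | Obtained | Lost of 9 |
|---|---|---|
| 6 weeks | 2 | 7 |
| 3 months | 3 | 6 |
| 6 months | 4 | 5 |
| 1 year | 5 | 4 |

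Functional and ultrasound measures are scheduled only to 1 year and are not counted here.

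**4. What the registry as a whole loses.** The documents give no rate of severe reactions, so this is scale only. *Sample size* gives a minimum of 500 participants, hence 500 × 9 = 4,500 scheduled scores. Assume that 1% to 6% are removed, that is 5 to 30 participants, between the 6-week and 1-year visits.

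- Low end: 5 × 4 = 20 scores; 20/4,500 = 0.4%.
- High end: 30 × 7 = 210 scores; 210/4,500 = 4.7%.

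The 1% and 6% are assumptions and have no basis in the protocol.

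**5. Whether the planned analysis repairs the loss.** Imputation under missing at random fills the later scores by taking removed participants to resemble those still followed, given their earlier data. If the rule is applied as written, every participant with a qualifying reaction leaves. There are then no later scores from such participants from which an imputation model could learn, even if it included the reaction as a variable. Complete-case analysis drops the same participants. It therefore cannot show whether their unseen scores are worse than those imputed.

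**The case against.** The strongest case against is that this is a wording defect with little demonstrated effect. The text does not literally say that data collection stops. If the registry assigns no intervention, the rule may seldom or never apply. If the word means study tests, these are questionnaires, imaging and physical tests, and treatment-related bias is unlikely. The consent pages are not in the available text and may contain terms for follow-up. A cheap fix does not by itself make a point more serious.

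Much of this stands, and it limits the point. Three stronger readings are tempting but not supported.

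- *That up to 5 years of rupture follow-up is lost.* The second research question models "subsequent acute rupture, with results reported as hazard ratios or odds ratios and 95"% confidence intervals, so rupture matters. But rupture is not a listed outcome, and no section describes how it is captured to 5 years. The removal rule cannot be shown to end a capture that was never set out.
- *That treatment comparisons are biased by a stated amount.* Any such figure needs reaction rates by treatment, a deficit in later scores, a standard deviation and group sizes. The protocol gives none of these, and the argument works only if the intervention means the treatment received.
- *That earlier data from removed participants are either kept or discarded.* The protocol gives general storage rules and says neither.

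What the objection does not remove is the rule itself. It is automatic and unqualified, and no section shown provides for follow-up afterwards. Staff who follow it as written would end the questionnaires.

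**Conclusion.** The point holds as a conflict within the protocol. A rule worded for an intervention trial sits in a registry with no assigned intervention and, read plainly, ends the planned self-reported follow-up of participants selected by a severe reaction. For each of them, 7 of 9 VISA-A scores are lost if removal follows the 6-week visit and 4 of 9 if it follows the 1-year visit. These counts rest only on the published schedule and on reading removal as the end of assessment.

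The number of participants affected is unknown and probably small, and no bias in any treatment comparison is shown. The point should still be fixed: the loss is irreversible, it is related to harm, and neither the planned imputation nor the complete-case analysis addresses it.

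**What to change.** Reconcile *Adverse events reporting and harms* with the registry design and the 5-year schedule.

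1. Define the intervention: treatment received, study assessments, or both. Align the terms used for the procedure and for study-related effects with that definition.
2. Separate two things that removal now merges: stopping a treatment or study test, and stopping data collection. The first is left to the clinicians and investigators, and no position is taken on it here. For the second, state that the already planned questionnaires continue to 5 years, and that data already collected are retained, unless the participant withdraws consent.

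No additional study tests are implied. The cost is a definition, a sentence or two in the protocol, slight extra questionnaire follow-up for what are probably few participants and, if the consent form does not already cover it, matching wording there. The change is best made before any such removal occurs, because missed assessments cannot be recreated.
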